13.5 Medication Use

Medication use is expected to fall within the guidelines established for treating COPD [40]. Study participants will be asked to provide information regarding their use of four classes of medications, including bronchodilators (beta-agonists, anticholinergics, methylxanthines), corticosteroids, antibiotics, and anti-inflammatories (e.g. statins, roflumilast). Addition of new medications in these classes or alterations in dose over the course of the study will be tracked. Study participants will be requested to bring all medication containers with them to each follow-up visit.

13.6 Daily Diary

The daily diary (hard-copy form) will be given to the study candidate at the baseline visit and collected at the bronchoscopy procedure visit and then electronically at the 45-day, 3-month, 6-month, 9-month, and 1-year follow-up visits.

Study participants will be asked to maintain a daily diary in which they will note compliance to the pulmonary rehabilitation program, complete the EXACT-PRO questionnaire, and note health status changes. They will be asked to complete the diary immediately before going to bed at night. Completion of the daily diary will begin on the first day after the bronchoscopy procedure and will be completed through the 1 year follow-up visit. Every effort will be made to ensure that study participants complete all diary entries, although failure to do so will not be considered a protocol deviation.

13.6.1 Pulmonary Rehabilitation Program Compliance

Study participants will be asked to self-report the number of exercises performed that day and the amount of time (minutes) spent doing them.

13.6.2 EXACT-PRO Questionnaire

The EXACT-PRO was developed to serve as a standardized outcome measure to evaluate COPD exacerbations [41]. Respondents are asked to self-report symptoms such as cough, mucous discharge, chest discomfort, and breathlessness. The questionnaire consists of 14 items, in which the patient grades the symptom as experienced by selecting one of five different responses (e.g. 'not at all', 'rarely', 'occasionally', 'frequently', 'almost constantly').

13.6.3 Health Status Changes

Health status changes data will consist of asking the study participant to self-report changes in maintenance medications, presence of emphysema symptoms, and whether or not they may have been deterred from their normal daily activities due to their emphysema symptoms.

13.7 Six-Minute Walk Distance (6MWD) Test

Six-minute walk distance testing will be performed according to the “ATS Statement” Guidelines for the Six-Minute Walk Test – March 2002” [42]. The test should be performed indoors, along a flat, straight, enclosed corridor with a hard surface that is seldom traveled. The walking course must be 30 meters in length. The length of the corridor should be marked every 3 meters. The turnaround points should be marked with a cone. A starting line, which marks the beginning and the end of each 60-meter lap, should be marked on the floor. The study participant should rate their baseline dyspnea and overall fatigue before the test and rate their dyspnea and overall fatigue after the test using the Borg scale. Required equipment, patient preparation, and measurements are specified in the ATS guidelines.

13.7.1 Dyspnea Assessment

Dyspnea and overall fatigue will be measured in all study participants using the Borg Scale [43,44] immediately prior to and immediately after performing the 6MWD test.

13.8 Blood Work

Blood chemistry variables collected during for the study will include arterial blood gases (ABGs), complete blood counts (CBCs), serum (or plasma) fibrinogen, plasma cotinine and/or arterial carboxyhemoglobin, and alpha-1 anti-trypsin deficiency.

13.8.1 Arterial Blood Gases (ABGs)

Blood gases should be collected with the study participant breathing room air. If the study participant is receiving supplemental oxygen at the time arterial blood gases are intended to be sampled, the supplemental oxygen should be discontinued for 10 minutes prior to sampling. If during this 10-minute period oxygen saturation falls below 80%, supplemental oxygen should be provided and increased in one liter/minute increments every three minutes until the minimum flow necessary to achieve 90% oxygen saturation is reached. Blood gases should then be sampled at this point. Subsequent blood gas samples should be taken under the same supplemental oxygen flow rate conditions.

13.8.2 Complete Blood Counts (CBCs)

Complete blood counts will be collected to characterize general health status.

13.8.3 Serum Fibrinogen

Blood fibrinogen is a measure of systemic inflammation. Increased levels have been shown to be associated with increased risk of COPD exacerbations [45].

13.8.4 Plasma Cotinine and/or Arterial Carboxyhemoglobin

Plasma cotinine and/or arterial carboxyhemoglobin counts will be collected to monitor nicotine use.

13.8.5 Alpha-1 Antitrypsin Protease Inhibitor Counts

Alpha-1 antitrypsin protease inhibitor counts will be used to assess screening eligibility criteria.

13.9 Chest X-Ray

Chest X-ray will be collected as specified in Section 14.0 and at any other time in which it may be considered medically necessary following the bronchoscopy procedure to screen for signs of volume reduction and pneumothorax.

13.10 Physical Exam

A routine medical examination will be performed as specified in Section 14.0.

13.11 High Resolution Computed Tomography

All attempts will be made to acquire volumetric high resolution computed tomography (HRCT) images using standardized methods across clinical sites at all times of acquisition. The CT scans should be obtained using the study CT acquisition protocol (see Appendix 6).

The screening CT study, collected for all study participants as part of the study screening process, will be considered the baseline CT for statistical analysis. Study investigators, in conjunction with the site-based radiologist(s) if desired, will evaluate CT images collected for study candidates during screening using an FDA approved software package to determine whether study candidates meet study eligibility criteria.

For study participants who receive the study treatment, post-bronchoscopy follow-up CT studies will be collected at the 45-day and 1-year visits. For study participants who receive the study treatment and undergo valve adjustment, an additional HRCT scan will be collected at the 3-month visit.

Clinical site personnel will transmit the CT studies in original DICOM format to a core reading laboratory who will assess the image quality of the studies and review and analyze the images. The CT images will be analyzed quantitatively using automated 510k cleared software and qualitatively, depending on the variable of interest, by the core reading laboratory.

The core reading laboratory will assess all HRCT scans to determine whether study participants who received the study treatment may be candidates for valve adjustment. This will be conducted by 1) determining volumetric change between the screening HRCT scan and post-procedure 45-day HRCT scans in the treated lobe and 2) evaluating valve placement in the target airways. For study participants who undergo a valve adjustment procedure, the 3-month CT scan will be assessed for volumetric change in the treated lobe; valve placement will also be evaluated. The 1-year HRCT scans will be assessed to determine target lobe volume reduction. In addition, the 1-year HRCT scans may be examined to assess valve placement for lobar occlusion and other radiographic features.

13.12 BODE Index

The BODE index is a multidimensional measure that has been reported to be predictive of risk of death from any cause and from respiratory causes [46,47]. It combines four measures frequently used in COPD studies as a composite score: body-mass index (BMI), obstruction (FEV_1 % predicted), dyspnea, usually characterized using the mMRC

survey score, and exercise capacity, as determined using the 6MWD test. Each component is graded and a score of 0 to 10 is obtained as indicated in the table below. The BODE Index will be calculated and reported in the final study report.

Table. Determination of the BODE Index Score.

	Points for BODE Index Score			
	0	1	2	3
BMI (kg.m ⁻²)	>21	≤21		
FEV1 % predicted	≥65	50-64	36-49	≤35
MMRC	0-1	2	3	4
6MWD (m)	≥350	250-349	150-249	≤149

14.0 SEQUENCE FOR TESTING

14.1 Screening Assessment – within 6 months prior to randomization

- Informed Consent
- Inclusion and Exclusion Criteria
- Medical History
- Vital Signs/Physical Exam
- Lung Function Testing (Study Protocol Section 13.0)
 - Spirometry (collected using your clinic’s normal care regime)
 - Body Plethysmography
 - Diffusing Capacity (DL_{co})
- HRCT Scan (Study Protocol Section 8.5.1, Appendix 6 and core lab Protocol)
 - In order for the study candidate to be found to meet the HRCT emphysema lobar destruction score criterion and the emphysema heterogeneity score criterion, the CT scan must be collected using the HRCT scan acquisition protocol
 - Full inspiratory scan (TLC)
 - Full expiratory scan (RV)
 - Forward CT scans to core lab of all candidates meeting the HRCT scan screening eligibility criteria
 - Forward the first 5 Myrian analyses (both (in)eligible candidates) to core lab to confirm proficiency for using the CT scan screening software
 - NOTE: A pre-existing CT scan that the study candidate provides to you or that is found during the chart screening may be “pre-screened” using the CT scan screening software.
- ECG
- 6-Minute Walk Distance (Study Protocol Section 13.7)
- Echocardiogram
- Blood Work (Study Protocol Section 13.8)
 - Arterial Blood Gases (ABGs)
 - Complete Blood Counts (CBCs)
 - Alpha-1 Antitrypsin Deficiency Test
 - Plasma Cotinine

- use Arterial Carboxyhemoglobin if candidate uses nicotine products)
- Serum Fibrinogen

If the Study Screening Eligibility Criteria are met by the Candidate, ask the Candidate to begin the Study Eligibility Pulmonary Rehabilitation Program (if the Study Candidate has already met the Pulmonary Rehabilitation Criterion you may proceed with the Baseline Visit)

14.2 Baseline Assessment - Conduct ≤ 120 days following screening eligibility

- Sign Participation Informed Consent (if only Screening Informed Consent was collected previously)
- Pulmonary Rehabilitation Eligibility Criterion Completed
 - At least 8 sessions (4 weeks with 2 sessions per week; Study Protocol Section 10.1)
- Spirometry
- 6-Minute Walk Distance (Study Protocol Section 13.7)

After confirmation of Baseline Eligibility:

- Vital Signs/Physical Exam
- Medication Use
- Vaccinations, if necessary (Pneumococcal, Influenza)
- Self-Reported Health Status Measures
 - SGRQ
 - SF-36
 - EQ-5D
 - BDI
 - mMRC
 - CAT
 - Health Care Utilization
- Daily Diary
 - Send paper diary home with study candidate to complete daily for 7 days prior to the scheduled bronchoscopy procedure
- Create Bronchoscopy Procedure Plan
- Contact Pulmonx and schedule Procedure date

14.3 Bronchoscopy Procedure – Should occur ≤ 60 days after baseline assessment visit

- **Pre-Procedure Orders and Preparation**
 - Female – pregnancy test, if applicable to informed consent
 - Ensure study personnel are identified for pneumothorax management

Recommended:

- Prophylactic antibiotic regimen may be initiated 2 days prior to procedure if desired by study investigator
- Corticosteroids may be initiated 2 days prior to procedure if desired by investigator

- Inhaled bronchodilator may be given 20 min prior to procedure
- Prior to the procedure, IV first or second generation antibiotics should be administered
- Record or collect photos of EBV placement

- **Bronchoscopy**
 - Anesthesia = conscious sedation with study candidate breathing spontaneously
 - Chartis System: assessment of target lobe collateral ventilation
 - After confirmation of study device eligibility criterion (finding of little or no collateral ventilation in targeted treatment lobe) proceed with randomization

- **Study Device Placement**
 - May convert study participant to general anesthesia
 - Record device lot numbers and valve placement location on worksheet

14.4 Post Procedure

- Study Treatment Arm:
 - Perform chest x-ray within 1 hour (\pm 30 minutes)
 - Monitor vital signs and pulse oximetry for first 24 hours
 - Collect ABGs and serum fibrinogen at 24 hours
 - Antibiotics
 - Bronchodilator Therapy
 - Perform chest X-rays daily x 5 days during hospital stay

- Control Arm:
 - Monitor vital signs and pulse oximetry until discharge
 - Collect ABGs and serum fibrinogen before discharge

14.5 Prior to Discharge

- Study Treatment Arm
 - Perform pre-discharge chest X-ray and physical examination
 - Schedule follow-up visits, including daily contact through 10 days
 - Bronchodilator inhaler, course of antibiotics, corticosteroids
 - Disburse Daily Diary
 - Provide Medical Alert Card, Treated Study Participant Bracelet, Transferring Instructions if Late Pneumothorax, and Post-Procedure Instructions
 - Adverse Event Assessment

- Control Arm
 - Schedule follow-up visits
 - Bronchodilator inhaler, course of antibiotics, corticosteroids
 - Disburse Daily Diary

14.6 Daily Follow Up Phone Call for 10 Days after Discharge (up to 11:59 pm)

- Study Treatment Arm
 - Symptom Checklist
 - Follow up may occur in hospital if subject is still hospitalized

14.7 Day 7 after Discharge Visit (+ 1 business day)

Study Treatment Arm Only

- Vital Signs/Physical Exam
- Chest X-ray
- Symptom Checklist
- Investigator to assess for return to regular activity and initiation of the protocol required pulmonary rehabilitation program
 - Assessment should show lack of evidence of pneumothorax, infection, or exacerbation, tolerance of light activities, and physical condition at least similar to or better than at the baseline visit
- Adverse Events assessment
- Symptom Checklist may be conducted during visit

14.8 Day 30 Visit (+/- 5 days)

Study Treatment Arm Only

- Vital Signs/Physical Exam
- Chest X-ray
- Adverse Events assessment

14.9 Day 45 Visit (+/- 5 days)

- Vital Signs/Physical Exam
- Medication Use
- Daily Diary Collection
- Spirometry
- Body Plethysmography
- DLco
- Collect mMRC Survey
- 6-Minute Walk Distance
- Adverse Event Assessment
- Study Treatment Arm
 - Chest X-ray
 - HRCT Scan (may be completed in a separate visit)
 - Forward CT scan to core lab

14.10 3 Month Visit (+/- 14 days)

- Vital Signs/Physical Exam

- Medication Use
- Daily Diary Collection
- Collect SGRQ Survey
- Collect Health Care Utilization Survey
- Collect TDI Survey
- Collect CAT Survey
- Study Treatment Arm
 - Only EBV treated participants who undergo valve adjustment -- may be completed in a separate visit
 - HRCT, forward CT scan to core lab
 - Chest X-ray
 - Body Plethysmography

14.11 6 Month Visit (+/- 21 days)

- Vital Signs/Physical Exam
- Medication Use
- Daily Diary Collection
- Spirometry
- Collect SGRQ Survey
- Collect Health Care Utilization Survey
- Collect mMRC Survey
- Collect TDI Survey
- Collect CAT Survey
- 6-Minute Walk Distance
- Adverse Event Assessment

14.12 9 Month Visit (+/- 21 days)

- Medication Use
- Daily Diary Collection
- Collect TDI Survey
- Collect CAT Survey
- Collect Health Care Utilization Survey

14.13 1 Year Visit (+/- 45 days)

- Vital Signs/Physical Exam
- Medication Use
- Daily Diary Collection
- Spirometry
- Collect SGRQ Survey
- Collect Health Care Utilization Survey
- Collect SF-36 Survey
- Collect EQ-5D Survey
- Body Plethysmography
- DL_{co}

- Collect TDI Survey
- Collect CAT Survey
- Collect mMRC Survey
- 6-Minute Walk Distance

The following may be completed in a separate visit or in order as scheduling permits after all other testing

- ECG
- Blood Work (ABGs, CBCs, plasma cotinine, serum fibrinogen)
- Adverse Event Assessment
- Study Treatment Arm
 - HRCT Scan for EBV treated participants
 - Forward CT scan to core lab
- Control Arm
 - After completing the 1-year visit testing, assess suitability for crossing over to study treatment.
 - The study investigator must document the participant's suitability for crossing over to study treatment; to qualify for crossover, a control arm participant must have been followed up successfully through 1 year and demonstrate lack of a clinically important response
 - The crossover procedure must be scheduled to occur within the next 60 days following the 1-year visit
 - After receiving the study treatment, the follow-up visits and testing at each visit will be identical to the schedule for treatment arm participants

14.14 Annual Visits (+/- 60) only for Study Participants treated with EBV

- Spirometry
- Adverse Event Assessment

15.0 SAFETY ELEMENTS

15.1 Adverse Events

Previous studies of emphysema patients who were followed longitudinally and treated using medical management [10,16,17], diagnostic or interventional bronchoscopy [448,49], or endobronchial valves [16,17] indicate that a moderate risk of adverse events may be anticipated during this study. Adverse events will be graded by defining their severity and relatedness to the study device.

It is anticipated that the rates for adverse events will be higher for the study treatment arm than control arm during the treatment period ('short', or day of the study procedure to 45 days) but that the rates for these occurrences will be similar for both study arms during the post-treatment period ('long', or 46 days to 1 year).

Adverse events that may be observed include:

- ❖ Cardiovascular events such as:
 - New onset cardiac arrhythmia
 - New diagnosis of congestive heart failure, which may be indicated by ≥ 1 -point increase in NYHA functional classification score
 - Acute myocardial infarct requiring medical care
 - New diagnosis transient ischemia attack (TIA) or stroke
 - New diagnosis deep vein thrombosis
 - Pulmonary embolism, which may be indicated by direct clinical evidence or V/Q evidence of segmental or larger perfusion defects

- ❖ COPD and Emphysema events such as:
 - COPD exacerbation requiring treatment with antibiotics and/or oral steroids
 - AECOPD requiring emergency room visit or hospitalization
 - Respiratory failure requiring re-intubation at any time during follow-up and/or invasive mechanical ventilation >24 hours after the bronchoscopy procedure
 - Pneumonia requiring treatment with antibiotics, indicated by consolidation on X-ray or CT scan and clinical characteristics of active infection (fever, leukocytosis, hypotension)

- ❖ Pulmonary / Thoracic events such as:
 - Hemoptysis requiring new evaluation or intervention
 - Pneumothorax indicated by clinical symptoms and/or X-ray
 - Pneumothorax requiring intervention
 - Empyema requiring new evaluation or intervention
 - Non-cardiac chest pain driving the study participant to seek medical care
 - Pleural effusion noted radiologically
 - Lung mass / cancer noted radiologically
 - Fractured rib noted radiologically
 - Laryngospasm driving the study participant to seek medical care
 - Dysphonia driving the study participant to seek medical care
 - Hypoxemia requiring increased or new oxygen use
 - Adverse tracheobronchial observations such as bronchial granulation tissue, bronchial ulceration, bronchial trauma

- ❖ Other events such as:
 - Death, any cause
 - Septicemia as evidenced by constitutional signs and symptoms consistent with bloodstream infection (with at least two separate blood cultures positive for the same pathogen(s), requiring systemic antimicrobial therapy)
 - Non-pulmonary infection requiring medical care
 - Fever > 99.5 °C for > 24 hours

- ❖ Endobronchial Valve events such as:
 - Valve expectoration, as reported by the study participant
 - Valve migration, as indicated by clinical and/or radiological evidence that a valve has left the target airway
 - Pneumonia distal to implanted valves, indicated by consolidation on X-ray or CT scan and clinical characteristics of active infection (fever, leukocytosis, hypotension)

15.2 Serious Adverse Events

An adverse event is considered serious if it meets the definition of a serious adverse event (SAE) as defined in Section 21.2. Serious adverse events may occur at any time during the study and will be reported as serious regardless of when they occur, provided they meet the definition of a serious adverse event.

15.3 Management of Selected Anticipated Adverse Events

15.3.1 Pneumothorax

Pneumothorax is an expected and anticipated event in patients undergoing a lung volume reduction procedure. With lung volume reduction surgery (LVRS), pneumothorax occurs in all (100%) cases and all patients leave the operating room with a chest tube(s) to manage air leaks. After EBV treatment, it is anticipated that the collapsed lung in the target lobe or expanding lung in adjacent lobe(s) may develop an air leak(s). With lung volume reduction procedures, achieving a higher success rate may be associated with having a higher risk of pneumothorax.

In the VENT study, pneumothorax was seen in 15%-20% of EBV-treated study participants who were thought to have little or no lobar CV (i.e. had HRCT suggestive of complete fissure) along with HRCT evidence of lobar occlusion with valve treatment. Therefore, it is anticipated in this study that approximately one in five of EBV-treated study participants may experience a post-procedure pneumothorax.

Study participants who received the study treatment will be provided with a Medical Alert Card, Treated Study Participant Bracelet, Transferring Instructions if Late Pneumothorax, and Post-Procedure Instructions prior to hospital discharge. Study participants who received the study treatment will be contacted during the 10 days after discharge and asked about increased chest pain, nausea, and new, worsening shortness of breath, which are all potential indicators of pneumothorax.

A suggested treatment plan for managing any suspected pneumothorax is provided in **Appendix 18**. Any study participant who has a persistent pneumothorax requiring care beyond a chest tube should be transferred to the treating hospital and attended to by the treating physician and his or her study team.

15.3.2 Pneumonia

Pneumonia-like symptoms, including low-grade fever, increased sputum, and radiographic abnormalities, are anticipated consequences of bronchoscopy. In this study, pneumonia will be defined as: 1) fever (≥ 99 °F) persisting for ≥ 48 hours and 2) white blood count $>15,000$ cells/mcL. Any study participant having clinical and radiological signs of pneumonia or pneumonia-like symptoms will be medically treated.

15.3.2.1 *Pneumonia Distal to Valve(s)*

Any study participant observed to have consolidation on X-ray or CT scan and clinical characteristics of active infection (fever,

leukocytosis, and hypotension) will be considered to have pneumonia distal to valve(s).

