19.2 Clinical Events Committee

The Clinical Events Committee (CEC) will consist of board-certified physicians who may be specialists in pulmonology, thoracic surgery, interventional pulmonology, or thoracic radiology who are not otherwise participating in the study (Note: The CEC members will be not be DSMB participants). The CEC will regularly review and adjudicate all serious and/or potentially device-related Adverse Events through at least the 1 year follow-up visit and may also conduct an annual review at 2, 3, 4, and 5 years.

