inter-lobar fissures	percent complete	percentage of participants

V. Adjustment for Potential Confounders

The covariates shown in Table 6 may be potentially influential with respect to the effectiveness endpoints. If any of these covariates are found to be out of balance between the groups (at the two-sided 0.10 level), they will be included in a multivariate analysis, along with an indicator of treatment group, to evaluate their potential effect on the study conclusions. A multivariate logistic regression model will be used for primary and secondary endpoints.

Table 6. Covariates

	Baseline	Procedure
Gender	X	
Age	X	
Clinical Site	X	
6MWD	X	
Patient-reported health status measures (e.g. SGRQ)	X	
Body Mass Index	X	
BODE Index	X	
Medication Use	X	
Residual Volume (RV)	X	
RV % Predicted	X	
Total Lung Capacity (TLC)	X	
TLC % Predicted	X	
RV/TLC	X	
IC/TLC	X	
Vital Capacity	X	
Forced Vital Capacity (FVC)	X	
FVC % Predicted	X	
FEV ₁	X	
FEV ₁ % Predicted	X	
FEV ₁ / FVC	X	
Lobar Volume	Х	
Lobar Destruction Scores	Х	
Ipsilateral DS Heterogeneity	X	
Severity of emphysema (GOLD classification)	X	
Comorbidities	X	
Target Treatment Lobe		Х
Treatment Group		Х

VI. Secondary Valve Procedures

Secondary valve procedures will be evaluated by examining the proportion of patients who undergo valve removal, valve replacement, or valve adjustment, and describing the reasons they occurred. Data for these study participants will be contrasted to data for study participants who did not receive a secondary valve procedure.

VII. Safety Analyses

Evaluation of the short- and long-term adverse events profile during the treatment period, defined as the day of the study procedure until 45 days after the study procedure (short), and in the post-treatment period, defined as 46 days after the study procedure until the 1-year follow-up visit (long). For the Control arm, the date of study procedure will be considered the date of the bronchoscopy assessment. Safety analyses will be performed by examining the percentage of patients that experiences adverse events. The rates and 95% exact confidence intervals will be presented on an event and on a per-patient basis. The percentage of subjects reporting adverse events occurring in at least 3% of subjects in either treatment arm will be compared using a Fisher's Exact test.

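### Pneumonia has two non-equivalent case definitions with no stated precedence, and the distal-to-valve category does not require the consolidation to lie in the valved lobe

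*Protocol*

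**What the plan says.** Protocol section 15.1, in its group of COPD and emphysema events, lists "Pneumonia requiring treatment with antibiotics, indicated by consolidation on X-ray or CT scan and clinical characteristics of active infection", with fever, leukocytosis and hypotension given as the characteristics. In a separate group of valve events it lists pneumonia distal to implanted valves, with the same imaging and infection criteria but no mention of antibiotics.

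Section 15.3.2 says "In this study, pneumonia will be defined as" fever of at least 99 °F for at least 48 hours together with a white count above 15,000 cells/mcL. Its subsection 15.3.2.1 then assigns the distal-to-valve label. The qualifying text is "Any study participant observed to have consolidation on X-ray or CT scan and clinical characteristics of active infection", again with fever, leukocytosis and hypotension. Section 15.4.2 names pneumonia and distal-to-valve pneumonia side by side as two conditions that may lead to valve removal.

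The treating investigator determines adverse events (section 21.1). The Clinical Events Committee will "adjudicate all serious and/or potentially device-related Adverse Events" (section 19.2). SAP section VII reports adverse event rates by period and states that "adverse events occurring in at least 3% of subjects in either treatment arm will be compared using a Fisher's Exact test". It also classifies treatment-arm events as device-related, procedure-related or neither. The SAP gives no case definition for pneumonia.

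**The concern.** Two sections of one protocol set out criteria for the same event, and the criteria differ in kind: one rests on imaging and treatment, the other on duration of fever and a white-count threshold. A site following section 15.1 and a site following section 15.3.2 would report different participants as having pneumonia.

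The valve-related category has its own problem. The protocol plainly intends it to be distinct from ordinary pneumonia, but its written criteria do not make the distinction. In an EBV participant, any consolidation with signs of infection satisfies it, wherever in the lungs it lies.

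At stake are the between-arm comparison of pneumonia, which the revised SAP introduced when it stopped limiting the safety endpoint to the EBV arm, and the count of a device-specific complication.

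**Working it through.** No figure in the plan depends on the pneumonia definition, so there is none to reproduce. The check is a comparison of criteria.

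| Criterion | 15.1 pneumonia | 15.3.2 pneumonia | 15.1 distal to valves | 15.3.2.1 distal to valves |
|---|---|---|---|---|
| Consolidation on imaging | required | not required | required | required |
| Fever | named, no duration | ≥99 °F for ≥48 h | named, no duration | named, no duration |
| White count | leukocytosis, no cut-off | >15,000 | leukocytosis, no cut-off | leukocytosis, no cut-off |
| Hypotension | named | not mentioned | named | named |
| Antibiotic treatment | required | not required | not mentioned | not mentioned |
| Location relative to valves | not applicable | not applicable | in the label only | in the label only |

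Four hypothetical cases show the consequences.

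1. Fever for 48 hours, white count 16,000, no consolidation: pneumonia under 15.3.2, not under 15.1.
2. Antibiotic-treated consolidation, fever for 24 hours, white count 12,000, hypotension: pneumonia under 15.1, not under 15.3.2. (I take 12,000 as leukocytosis because Appendix 5 treats a count above 10,000 as elevated.)
3. Antibiotic-treated consolidation, fever for 48 hours, white count 16,000, hypotension: pneumonia under both.
4. An EBV participant with valves in the left lung and case 2 in the right lung: pneumonia under 15.1, and also distal to valves on the criteria of 15.3.2.1. Only one lung is treated (section 8.7.1), so this consolidation cannot be distal to a valve.

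Cases 1 and 2 show that neither definition contains the other. Case 3 shows that they overlap. Case 4 shows the misclassification in the valve category.

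*Ascertainment by arm (Appendix 12).* EBV participants have chest X-rays on Days 0 to 5, 7 days after discharge, at 30 days and at 45 days, and CT at 45 days and 1 year. The control schedule contains no follow-up chest imaging, although section 13.9 allows a chest X-ray at any time if medically necessary. After screening, complete blood counts are scheduled only at 1 year, in both arms. A definition that needs consolidation therefore draws on scheduled tests in one arm only. A definition that needs a white count depends almost wholly on unscheduled tests in both arms.

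*Illustration with assumed counts.* The exact arm sizes are not given. With 190 enrolled at 2:1, 190 × 2/3 ≈ 127 and 190/3 ≈ 63. All event counts and rates here are invented.

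- 18/127 (14.2%) against 2/63 (3.2%) gives Fisher p = 0.023. 14/127 (11.0%) against 2/63 gives p = 0.095. 9/127 (7.1%) against 2/63 gives p = 0.34.
- Suppose the broader definition gave true rates of 15% and 3%, and a narrower one caught 100, 75, 50 or 25% of those cases in both arms. The chance of p ≤ 0.05 is then 74, 56, 30 and 3%.
- From 12% and 4% it is 38, 25, 11.5 and 1%. From 10% and 5% it is 15, 10, 4 and 0.5%.

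These figures show that the test is sensitive to the definition if pneumonia is common enough. They do not estimate what would happen in this trial.

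**The case against.** The strongest reply is that section 15.1 is an illustrative list of events that may be seen, whereas only section 15.3.2 uses defining language, so 15.3.2 governs. That is a fair basis for precedence. But 15.1 carries its own diagnostic criteria, no clause ranks the two sections, and 15.3.2.1, inside the same subsection, returns to the consolidation criteria.

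A second reply is adjudication. Fatal, life-threatening and hospitalised cases are serious (section 21.2), and any potentially device-related case is also reviewed, so many pneumonias will reach the committee. This reduces the problem. It leaves out non-serious cases not thought device-related, and the protocol does not say which definition the committee applies. That may be settled in working papers outside these documents.

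Third, nothing decisive rests on pneumonia. Study success is an FEV₁ comparison, safety has no pneumonia hypothesis or limit, and the SAP allows events to be grouped into clinical categories. This stands and limits the severity.

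A reader might go further in two ways that the documents do not support.

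- One is that controls would be counted as having distal-to-valve pneumonia, because 15.3.2.1 speaks of any participant. Its heading, the valve-event grouping in 15.1 and the valve-removal context of 15.4.2 rule that out: a control has no valve.
- The other is that a definition without imaging would count reactions to the procedure as pneumonia, unequally between arms. Section 15.3.2 itself lists radiographic abnormalities among the expected consequences of bronchoscopy, so imaging does not clearly separate the two, and controls also undergo bronchoscopy.

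**Conclusion.** The point holds as an internal inconsistency of minor to moderate severity; the text is wrong as written. The two pneumonia definitions are non-equivalent and non-nested, though not mutually exclusive. The distal-to-valve criteria would class ordinary or contralateral pneumonia in an EBV participant as a valve event. The rates and tests in SAP section VII and the device-specific count inherit both problems, as does the crossover comparison of serious adverse events in SAP section X where pneumonia is serious.

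Because scheduled chest imaging after the procedure is in the EBV arm only, the choice of definition may change ascertainment differently by arm. Neither the direction nor the size can be derived from the documents. It is tempting to measure the problem by how few cases bring an event to the 3% testing threshold, but that is a property of the rule for every event type and says nothing about how many cases the two definitions classify differently.

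The conclusion rests on the written text and on there being no overriding definition in committee papers that are not public. The primary endpoint, its alpha and the sample size are untouched.

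**What to change.** Reconcile sections 15.1, 15.3.2 and 15.3.2.1 into one pneumonia case definition, applied in both arms by sites, the Clinical Events Committee and the SAP tables. Which clinical criteria it contains is for the sponsor and the committee to settle. Separate distal-to-valve pneumonia from other pneumonia by a recorded location relative to the implanted valves, in EBV-treated participants only (crossovers included), and say whether one event may appear in both categories.

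The cost is a change of wording in the protocol, committee charter and SAP, plus a query of cases already reported. All 190 participants were enrolled by the October 2017 SAP, so reclassification carries a risk of post hoc bias. To limit it, fix the definition first and have the committee classify the reported cases under it, ideally without reference to arm except for the valve-location item. The change remains useful for later data, since adverse events are collected to 5 years in EBV-treated participants.
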